7.2.5.2. Central Laboratory Measurements

Table 18 outlines the clinical laboratory measurements that will be reviewed at the central laboratory as specified in the Central Laboratory Manual.

Table 18: Central Laboratory Parameters

Panel	Parameters
Cytokines	TNF α , IL-2, IL-4, IL-6, IL-8, IL-10, IL-12p70, IL-13, IL1 β , IL1RA, IL2RA, and IFN γ
qPCR	
Tumor tissue quantitative polymerase chain reaction (qPCR) from fine needle aspirate and whole bloodqPCR from blood cultures
Other	Blood samples collected for exploratory analyses in preservation tubes

7.2.6. Electrocardiograms

Semi-supine single 12-lead ECGs will be performed at screening and reviewed locally.

7.2.7. Multi-gated Acquisition Scan or Echocardiogram

MUGA or ECHO will be performed within 6 months prior to the first dose of study treatment provided the patient has not received any potential cardiotoxic agents in the intervening period. If potential cardiotoxic agents have been administered within 6 months, patients must undergo a MUGA/ECHO during the screening period.

7.3. Efficacy Assessments

Disease response status will be assessed in the SYNB1891-injected lesion(s), and an overall analysis of potential responses in up to 5 noninjected target lesions will be performed using appropriate imaging at screening and every 2 cycles on study (i.e., at the end of every even-numbered cycle) for the duration of the treatment period and at the EOT visit (unless imaging has been performed within 8 weeks prior to the EOT visit). Every effort should be made to assess each lesion that is measured at screening using the same imaging method(s) throughout the study to enable a consistent comparison. Injected lesions that are reduced in size on study to the extent that they are no longer able to sustain injections will continue to be monitored for response.

Tumor response will be evaluated by the local Investigator using appropriate imaging in accordance with RECIST 1.1 ([Eisenhauer et al 2009](#) and [Appendix 1](#)), iRECIST ([Seymour et al 2017](#) and [Appendix 2](#)), and/or LYRIC ([Cheson et al 2016](#) and [Appendix 3](#)).

7.4. Pharmacodynamic Assessments

Blood samples for qPCR will be collected during the first 24-hour period of Cycle 1 and will be analyzed to assess for the presence of circulating SYNB1891.

An FNA of the eligible lesion will be performed predose on Cycle 1 Day 1 (within 7 days prior to Cycle 1 Day 1) and predose on Cycle 1 Day 8 and analyzed for bacterial kinetics by qPCR.

Core biopsies of the intended SYNB1891-injected lesion will be performed predose on Cycle 1 Day 1 (within 7 days prior) and predose on Cycle 2 Day 1 (within 3 days prior). For patients who withdraw from the study prior to Cycle 2 Day 1, the second biopsy should be performed at the EOT visit (see Section [7.5.1](#)). While not required for study entry, second biopsiable lesions, if present, will undergo a mandatory biopsy at the same time points.

To optimize the quality of the biopsy samples obtained, 3 core samples should be obtained at each time point for each lesion, when feasible in the opinion of the Investigator. Biopsy tissue will be evaluated at various time points for IFN-responsive cytokines, TILs, PD-1, and PD-L1. Refer to the study manuals for details on the procedures for collecting, shipping, and handling biopsy material.

7.5. Follow-up Assessments

7.5.1. End-of-Treatment Visit

Within 14 days after the last dose of study treatment (or premature treatment discontinuation), an EOT visit will be performed and every effort should be made to perform the procedures specified in [Table 19](#) and [Table 20](#).

7.5.2. Safety Follow-up Visit

All patients will attend a Safety Follow-up visit 30 ± 5 days after the last dose of study treatment.

7.6. Sample Retention for Exploratory Analyses

De-identified blood samples may be stored for future analyses related to cancer and immune responses for up to 5 years from the time the sample is collected. Any unused samples will be destroyed.

Table 19: Schedule of Events (Arm 1)

Study Period	Protocol Section	Screening	Cycle 1							Cycles 2-4	Additional Cycles ¹	EOT/Early Termination Visit	Safety Follow-up Visit
Study Day	7	-28 to 0	1			2 (24 ± 2 hours postdose)	3 (48 ± 2 hours postdose)	8 ± 1 day	15 ± 1 day	1 ± 1 day	1 ± 1 day	Within 14 days after last dose	30 ± 5 days after last dose
			Baseline (predose)	Dose	(6 ± 1 hours postdose)								
Informed consent/enrollment	7.1	●											
Medical history	7.2.1	●											
Physical examination	7.2.4	●	●			●		●	●	●	●	●	●
Height	7.2.4	●											
Weight	7.2.4	●	●			●				●	●	●	●
Vital signs (blood pressure, body temperature, pulse, and pulse oximetry) ²	7.2.3	●	●		●	●		●	●	●	●	●	●
Screening for hepatitis B, C and HIV	7.2.5	●											
ECGs	7.2.6	●											
MUGA/ECHO	7.2.7	●											
Hematology (CBC with differential)	7.2.5.1	●	●					●	●	●	●	●	●
Blood chemistry, including LFTs	7.2.5.1	●	●					●	●	●	●	●	●
Coagulation (PT/aPTT)	7.2.5.1	●	●					●	●	●	●	●	●
Thyroid function (FT4, TSH)	7.2.5.1	●								● ³	● ³	●	
Urinalysis	7.2.5.1	●											
Cytokine blood draw	7.2.5.2		●		●	●		● ⁴	● ⁴	● ⁴		●	
Blood preservation tube for exploratory analyses	7.2.5.2		●					● ⁵		● ^{5,6}			
Kinetics of SYNB1891 (qPCR blood assay)	7.4		●		●	●							
Serum hCG (women of childbearing potential)	7.2.5	●											
Urine hCG (women of childbearing potential)	7.2.5		●							●	●	●	
Telephone call	7.2.2						●						
Fine needle aspirate of eligible lesion pre-injection	7.4		● ⁷					● ⁵					

Study Period	Protocol Section	Screening	Cycle 1							Cycles 2-4	Additional Cycles ¹	EOT/Early Termination Visit	Safety Follow-up Visit
Study Day	7	-28 to 0	1		2 (24 ± 2 hours postdose)	3 (48 ± 2 hours postdose)	8 ± 1 day	15 ± 1 day	1 ± 1 day	1 ± 1 day	Within 14 days after last dose	30 ± 5 days after last dose	
			Baseline (predose)	Dose									
Biopsy of eligible lesion	7.4		● ⁷						● ⁸			● ⁹	
Biopsy of noninjected lesion (if applicable)	7.4		● ⁷						● ⁸			● ⁹	
Administration of SYNB1891 intratumorally	4.2			●				●	●	●	●		
Tumor response using appropriate imaging	7.3	●							● ¹⁰	● ¹⁰	●		
Adverse event reporting	7.2.2		Continuously from the time of informed consent through the Safety Follow-up visit										
Monitoring for symptoms and signs of infection	7.2.2.1		Continuously from the time of informed consent through the Safety Follow-up visit										

Abbreviations: aPTT = activated partial thromboplastin time; CBC = complete blood count; ECG = electrocardiogram; ECHO = echocardiogram; EOT = end of treatment; FT4 = free thyroxine; hCG = human chorionic gonadotropin; HIV = human immunodeficiency virus; LFT = liver function test; MUGA = multi-gated acquisition; qPCR = quantitative polymerase chain reaction; PT = prothrombin time; TSH = thyroid stimulating hormone

¹ Patients who do not have progressive disease (i.e., those who achieve and sustain a complete/partial response or stable disease) may receive additional cycles of SYNB1891 given on Day 1 of each cycle for up to 24 months (i.e., Cycles 5 to 35) after the initial dose of study treatment until documentation of progressive disease or other discontinuation criteria, satisfaction of a predefined stopping rule, or no eligible lesions remain.

² Collected while patients are in a seated or supine position at screening, on Cycle 1 Day 1 (predose and 30 minutes, 1 hour, 2 hours, 3 hours, 6 hours, and 24 hours postdose), on all other study treatment days (predose and 30 minutes, 1 hour, 2 hours, 3 hours, and 6 hours postdose), at EOT/Early Termination and Safety Follow-up, and as clinically indicated.

NOTE: A ± 15-minute window is permitted for each timepoint.

³ Day 1 of odd-numbered cycles only.

⁴ Predose and 6 hours postdose (as indicated) after every SYNB1891 injection.

⁵ Predose.

⁶ Day 1 of Cycle 3 only.

⁷ The predose (baseline) biopsies and fine needle aspirate may be performed up to 7 days prior to Cycle 1 Day 1.

⁸ Core biopsies will be collected predose on (or up to 3 days prior to) Day 1 of Cycle 2 only (i.e., not Day 1 of Cycles 3 or 4).

⁹ For patients who withdraw from the study prior to Cycle 2 Day 1, the second biopsy should be performed at the EOT visit.

¹⁰ At the end of even-numbered cycles only.

Table 20: Schedule of Events (Arm 2)

Study Period	Protocol Section	Screening	Cycle 1							Cycles 2-4	Additional Cycles ¹	EOT/Early Termination Visit	Safety Follow-up Visit
			1		Dose	(6 ± 1 hours postdose)	2 (24 ± 2 hours postdose)	3 (48 ± 2 hours postdose)	8 ± 1 day	15 ± 1 day	1 ± 1 day		
Study Day	7	-28 to 0	Baseline (predose)										
Informed consent/enrollment	7.1	●											
Medical history	7.2.1	●											
Physical examination	7.2.4	●	●				●		●	●	●	●	●
Height	7.2.4	●											
Weight	7.2.4	●	●							●	●	●	●
Vital signs (blood pressure, body temperature, pulse, and pulse oximetry) ²	7.2.3	●	●			●	●		●	●	●	●	●
Screening for hepatitis B, C and HIV	7.2.5	●											
ECGs	7.2.6	●											
MUGA/ECHO	7.2.7	●											
Hematology (CBC with differential)	7.2.5.1	●	●						●	●	●	●	●
Blood chemistry, including LFTs	7.2.5.1	●	●						●	●	●	●	●
Coagulation (PT/aPTT)	7.2.5.1	●	●						●	●	●	●	●
Thyroid function (FT4, TSH)	7.2.5.1	●								● ³	● ³	●	
Urinalysis	7.2.5.1	●											
Cytokine blood draw	7.2.5.2		●			●	●		● ⁴	● ⁴	● ⁴		●
Blood preservation tube for exploratory analyses	7.2.5.2		●						● ⁵		● ^{5,6}		
Kinetics of SYNB1891 (qPCR blood assay)	7.4		●			●	●						
Serum hCG (women of childbearing potential)	7.2.5	●											
Urine hCG (women of childbearing potential)	7.2.5		●							●	●	●	
Telephone call	7.2.2							●					
Fine needle aspirate of eligible lesion pre-injection	7.4		● ⁷						● ⁵				
Biopsy of eligible lesion	7.4		● ⁷							● ⁸		● ⁹	

Study Period	Protocol Section	Screening	Cycle 1							Cycles 2-4	Additional Cycles ¹	EOT/Early Termination Visit	Safety Follow-up Visit
			1		Dose	(6 ± 1 hours postdose)	2 (24 ± 2 hours postdose)	3 (48 ± 2 hours postdose)	8 ± 1 day	15 ± 1 day	1 ± 1 day	1 ± 1 day	
Study Day	7	-28 to 0	Baseline (predose)										
Biopsy of noninjected lesion (if applicable)	7.4		● ⁷							● ⁸		● ⁹	
Administration of SYNB1891 intratumorally	4.2			●					●	●	●	●	
Administration of atezolizumab by IV infusion	4.2			●						●	●		
Tumor response using appropriate imaging	7.3	●								● ¹⁰	● ¹⁰	●	
Adverse event reporting	7.2.2		Continuously from the time of informed consent through the Safety Follow-up visit										
Monitoring for symptoms and signs of infection	7.2.2.1		Continuously from the time of informed consent through the Safety Follow-up visit										

Abbreviations: aPTT = activated partial thromboplastin time; CBC = complete blood count; ECG = electrocardiogram; ECHO = echocardiogram; EOT = end of treatment; FT4 = free thyroxine; hCG = human chorionic gonadotropin; HIV = human immunodeficiency virus; IV = intravenous; LFT = liver function test; MUGA = multi-gated acquisition; qPCR = quantitative polymerase chain reaction; PT = prothrombin time; TSH = thyroid stimulating hormone

¹ Patients who do not have progressive disease (i.e., those who achieve and sustain a complete/partial response or stable disease) at the end of Cycle 4 on combination therapy may receive additional cycles of study treatment for up to 24 months (i.e., Cycles 5 to 35) after the initial dose of study treatment until documentation of progressive disease or other discontinuation criteria, satisfaction of a predefined stopping rule, or no eligible lesions remain.

² Collected while patients are in a seated or supine position at screening, on Cycle 1 Day 1 (predose and 30 minutes, 1 hour, 2 hours, 3 hours, 6 hours, and 24 hours postdose), on all other study treatment days (predose and 30 minutes, 1 hour, 2 hours, 3 hours, and 6 hours postdose), at EOT/Early Termination and Safety Follow-up, and as clinically indicated.

NOTE: A ± 15-minute window is permitted for each timepoint.

³ Day 1 of odd-numbered cycles only.

⁴ Predose and 6 hours postdose (as indicated) after every SYNB1891 injection.

⁵ Predose.

⁶ Day 1 of Cycle 3 only.

⁷ The predose (baseline) biopsies and fine needle aspirate may be performed up to 7 days prior to Cycle 1 Day 1.

⁸ Core biopsies will be collected predose on (or up to 3 days prior to) Day 1 of Cycle 2 only (i.e., not Day 1 of Cycles 3 or 4).

⁹ For patients who withdraw from the study prior to Cycle 2 Day 1, the second biopsy should be performed at the EOT visit.

¹⁰ At the end of even-numbered cycles only.

8. STUDY DISCONTINUATION

8.1. Sponsor Discontinuation Criteria

This study may be discontinued at any time due to safety concerns (including, but not limited to, the stopping rules described in [Section 4.5](#)), failure to meet expected enrollment goals, administrative reasons, or at the discretion of the Sponsor. Should the study be terminated prematurely, the Sponsor will provide written notification to the Investigator and regulatory authorities and will specify the reason(s) for early termination. The Investigator must inform the IRB promptly and provide the reason(s) for the termination.

8.2. Study Discontinuation for Individual Patients

Determination of whether a patient should discontinue further study treatment administration and withdraw from the study will depend on whether one of the following qualifying events (except for withdrawal of consent) occurs prior to or after the patient receives SYNB1891:

- The patient withdraws consent.
- The Investigator or Sponsor notes a significant noncompliance with protocol procedures.
- The Investigator determines that the patient must discontinue further study dosing for medical reasons.
- Discontinuation of treatment with SYNB1891 may be considered for participants in whom all eligible injected lesion have undergone complete regression and are no longer injectable (at the discretion of the Investigator). In Arm 1, patients will continue in follow-up and in Arm 2, patients may continue on atezolizumab.
- Discontinuation of treatment with atezolizumab may be considered for participants who have attained a confirmed CR and have been treated for at least 8 cycles (at least 24 weeks), receiving at least 2 doses of atezolizumab beyond the date when the initial CR was declared. It is anticipated that these participants will have discontinued SYNB1891.

In patients who meet the criteria for permanent discontinuation due to intolerable toxicity, resumption of study treatment may be considered if the patient is deriving benefit and has fully recovered from the immune-related event. Patients can be re-challenged with study treatment only after approval has been documented by both the Investigator (or an appropriate delegate) and the Sponsor.

Patients may withdraw their consent at any time for any reason without prejudice to their future medical care by the physician or at the institution. If a patient withdraws consent, the date and stated reason for consent withdrawal should be documented. Patient data collected up to the date of consent withdrawal will be included in the analyses.

Patients who withdraw from the study prior to receiving the first dose of study treatment are not required to complete any further visits. Patients who withdraw from the study after receiving the first dose of study treatment must complete the EOT and Safety Follow-up visits, unless consent for follow-up is withdrawn. Patients who discontinue study treatment and withdraw from the

study will not be allowed to enroll again at a later date. If a patient who withdraws from the study has an ongoing SAE, every effort will be made to follow the SAE until the event has resolved, stabilized, or returned to baseline status. The Sponsor must be notified of all study withdrawals within 24 hours.

8.2.1. Patient Replacement

Patients who terminate participation in the study for any reason other than DLTs prior to receiving the second injection of SYNB1891 in Cycle 1 will be considered ineligible for the safety assessment required for dose-escalation decisions and may be replaced.

9. ADVERSE EVENTS

9.1. Adverse Event

An AE is any untoward medical occurrence, including the exacerbation of a pre-existing condition, in a patient administered a pharmaceutical product, regardless of causality.

9.1.1. Assessment of Severity

The severity rating of an AE refers to its intensity. The severity of each AE will be categorized using the NCI CTCAE, version 5.0 ([US DHHS 2017](#)). For any term that is not specifically listed in the CTCAE scale, intensity should be assigned a grade of 1 through 5 using the following CTCAE guidelines:

- Grade 1: Mild; asymptomatic or mild symptoms; clinical or diagnostic observations only; intervention not indicated
- Grade 2: Moderate; minimal, local or noninvasive intervention indicated; limiting age-appropriate instrumental activities of daily living
- Grade 3: Severe or medically significant but not immediately life-threatening; hospitalization or prolongation of hospitalization indicated; disabling; limiting self-care activities of daily living
- Grade 4: Life-threatening consequences; urgent intervention indicated
- Grade 5: Death related to AE

9.1.2. Assessment of Causality

Medical judgment should be used to determine the cause of the AE, considering all relevant factors such as (but not limited to) the underlying study indication, coexisting disease, concomitant medication, relevant history, pattern of the AE, temporal relationship to study treatment (with separate causality assessments for SYNB1891 and atezolizumab), and de-challenge or re-challenge.

Yes (possibly, probably, or definitely related): there is a reasonable possibility that study treatment caused the event; one or more of the following criteria apply:

- The event follows a reasonable temporal sequence from administration of study treatment.
- The event could not be reasonably attributed to the known characteristics of the patient's clinical state, environmental or toxic factors, or other modes of therapy administered to the patient.
- The event follows a known pattern of response to study treatment.
- The event disappears or decreases on cessation or reduction in dose. (It should be noted that in some situations an AE will not disappear or decrease in intensity upon discontinuation of study dosing despite other clear indications of relatedness).

No (unlikely, probably not related, or definitely not related): there is no reasonable possibility that study treatment caused the event; one or more of the following criteria apply:

- The event does not follow a reasonable temporal sequence from administration of study treatment.
- The event could be reasonably attributed to the known characteristics of the patient's clinical state, concurrent illness, environmental or toxic factors, or other modes of therapy administered to the patient.
- The event does not follow a known pattern of response to study treatment.
- The event does not disappear or decrease on cessation or reduction in dose(ing), and it does not reappear or worsen when dosing is resumed.

9.2. Serious Adverse Event

An SAE is any untoward medical occurrence that meets any of the following criteria:

- Results in death.
- Is immediately life-threatening (refers to an event in which the patient is at risk of death at the time of the event; it does not refer to an event, which hypothetically might have caused death if it were more severe).
- Requires inpatient hospitalization or prolongation of existing hospitalization.
- Results in a persistent or significant incapacity or substantial disruption of the ability to conduct normal life functions.
- Is a congenital anomaly/birth defect.
- Based on appropriate medical judgment, represents an important medical event that may jeopardize the patient or may require intervention to prevent one of the other outcomes described above.

9.2.1. Clarification of Serious Adverse Event Definition

- Progression of malignancy should be documented through appropriate methodology (e.g., as per iRECIST) and designated as progression of disease in the disease assessment eCRF, but should not be reported as an AE/SAE unless a causal relationship to study treatment is suspected.
- Death is an outcome of an SAE and not an SAE in itself. When death is an outcome, the event(s) resulting in death should be reported (e.g., "pulmonary embolism" with a fatal outcome). The appropriate diagnosis or term should be recorded and assigned severity Grade 5.
- In instances of death due ultimately to the underlying disease, the cause of death should be indicated as the specific event or condition resulting in death to the extent possible. If no appropriate term with a Grade 5 severity in the CTCAE can be identified, then a term should be selected from the CTCAE category "Death".

- “Life-threatening” means that the patient was at immediate risk of death from the event as it occurred. This does not include an event that might have led to death if it had occurred with greater severity. Grade 4 events (e.g., thrombocytopenia) are not always serious unless they have life-threatening consequences or result in hospitalization.
- Preplanned or elective hospitalizations including social and/or convenience situations (e.g., respite care) are excluded from SAE reporting. In addition, “admissions” under 23-hour observation or emergency room visits are excluded from SAE reporting; however, such events should still be reported on the appropriate eCRF page.
- Overdose of either study treatment or concomitant medication without any overdose signs or symptoms unless the event meets SAE criteria (e.g., hospitalization) are excluded from SAE reporting; however, such events should still be reported on the appropriate eCRF page.
- SAEs that occur within the safety follow-up period but are related to subsequent therapies are excluded from SAE reporting:
 - Patients who have completed study treatment administration or who terminate from the study and then undergo subsequent therapies during the safety follow-up period and experience an SAE specifically related to the administration of the subsequent therapy will not have those events reported as SAEs. This exclusion will include “elective” hospitalizations necessary for the administration of such therapies.

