9.4. Reporting of Adverse Events

All AEs, serious and nonserious, will be fully documented on the appropriate eCRF. For each AE, the Investigator must provide its duration (start and end dates or ongoing), intensity, assessment of causality, and whether specific action or therapy was required.

All AEs occurring from the time a patient signs informed consent through the Safety Follow-up visit must be recorded on the eCRF.

All SAEs, regardless of relationship to study treatment, must be reported to the Sponsor within 24 hours of the Investigator's knowledge. This should be done by faxing the completed SAE Report Form to the Sponsor at the number provided on the SAE Report Form. After the Safety Follow-up visit, only SAEs that are considered related to study treatment will be recorded, if clinically indicated.

Investigators must follow patients with AEs/SAEs until event resolution or stabilization, withdrawal of consent, patient loss to follow-up, or death, whichever occurs first.

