11. DATA RECORDING, RETENTION AND MONITORING

11.1. Case Report Forms

Data will be collected using source documents through an electronic data capture (EDC) system at the clinical site. The Investigator or designee will record data specified in the protocol using eCRFs. Changes or corrections to eCRFs will be made by the Investigator or an authorized member of the study staff according to the eCRF completion guidelines. It is expected that the site will enter all data within 5 days of a patient visit.

It is the Investigator's responsibility to ensure eCRFs are complete and accurate, regardless of whether this responsibility has been delegated in whole or in part. Following review and approval, the Investigator or designee will electronically sign and date the pages, which certifies that the Investigator has thoroughly reviewed and confirmed all data on the eCRF.

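### The SAE clarification excludes emergency room and 23-hour observation cases without an exception for events that are serious on other grounds, which conflicts with the SAE definition

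*Protocol*

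**What the plan says.** Protocol Section 9.2 lists the criteria for a serious adverse event and requires only one of them. Inpatient hospitalization is one. Being immediately life-threatening is another. A third covers an event that, on medical judgment, "represents an important medical event that may jeopardize the patient or may require intervention to prevent one of the other outcomes described above". None of these three depends on the others, and the life-threatening and important-medical-event criteria do not mention place of care.

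Section 9.2.1 is headed as a clarification of that definition. One bullet opens with planned stays: "Preplanned or elective hospitalizations including social and/or convenience situations (e.g., respite care) are excluded from SAE reporting". It then adds that admissions (the protocol puts that word in quotation marks) "under 23-hour observation or emergency room visits are excluded from SAE reporting; however, such events should still be reported on the appropriate eCRF page". The next bullet excludes overdoses "without any overdose signs or symptoms unless the event meets SAE criteria (e.g., hospitalization) are excluded from SAE reporting".

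Section 9.4 sets the time limit for serious events: "All SAEs, regardless of relationship to study treatment, must be reported to the Sponsor within 24 hours of the" Investigator's knowledge. For data entered on the eCRF, Section 11.1 says: "It is expected that the site will enter all data within 5 days of a patient visit".

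**The concern.** An investigator who follows Section 9.2.1 as written has grounds to enter an emergency room case on the eCRF and file no SAE report, even if the event was life-threatening. Section 9.2 tells the same investigator that the event is serious.

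The conflict matters because such care is foreseeable in this trial. SYNB1891 is a live bacterial product in its first clinical study. After the Sentinel patient's first dose, injections are given to outpatients who are observed for at least 6 hours (Section 4.2.2). Atezolizumab infusion reactions are described as occurring within 24 hours (Section 4.4.2.7), so possibly after the patient has gone home. Section 7.2.2.1 plans for infections treated locally by giving patients an identification card with study contact details.

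Three things depend on the event being classed as serious: the 24-hour notice to the Sponsor (9.4), SUSAR identification (9.2.2), and the serious TEAE tables (SAP Appendix 5, Tables 26-28). The SAP has no SAE definition of its own that would restore the exception.

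**Working it through.** The plan gives no figure to reproduce, so the check is a comparison of texts plus one comparison of reporting times.

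**1. Does any exclusion in Section 9.2.1 carry an exception?**
- Disease progression: yes, when a causal relationship to study treatment is suspected.
- Planned, elective or social hospitalization: no, but here the reason for the stay is not an acute event.
- Emergency room visit or 23-hour observation: no.
- Overdose without signs or symptoms: yes, "unless the event meets SAE criteria (e.g., hospitalization) are excluded from SAE reporting".
- SAEs related to a subsequent therapy: no, but the exclusion is limited to events caused by that other therapy.

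The emergency room and observation sentence is therefore the only exclusion that can cover an acute reaction to study treatment and has no exception.

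**2. Does other text restore the exception?** The bullet on Grade 4 events says that they "are not always serious unless they have life-threatening consequences or result in hospitalization". This treats life-threatening consequences as separate from hospitalization, but it does not qualify the emergency room sentence. Sections 9.2.2, 9.3 and 9.4 and SAP Section VIII.C contain no such text.

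**3. Is there another 24-hour route?**
- Adverse events of special interest (9.3), which include cytokine release syndrome (CRS): ongoing monitoring is required, with no time limit.
- Sentinel review (4.2.2): on or after Day 7.
- Grade 3 CRS with SYNB1891 (Table 2): Sponsor discussion before treatment resumes.
- Grade 3 or 4 infusion reaction or CRS with atezolizumab (Table 9): contact with the Medical Monitor, with no time limit.
- Medical Monitor review (9.7): ongoing. It could pick up an eCRF-only event, but no time limit or re-check of seriousness is stated.
- Safety Review Committee (9.7): after all patients in a cohort complete Cycle 1.
- Day 2 visit and Day 3 call (Tables 19 and 20): site contact after the first Cycle 1 dose only.

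None of these sets a 24-hour limit or classes the event as serious.

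**4. Reporting times.** For an SAE the limit is 24 hours = 1 day from the Investigator's knowledge. For an eCRF-only event, entry is expected within 5 days of a patient visit. If both clocks start on the same day, the difference is 5 − 1 = 4 days.

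The difference is larger only under two assumptions: that an outside emergency room attendance is not a study visit, and that the site knows of the event but enters it after the next scheduled visit. Cycle 1 injections are 7 days apart, so entry could then come as late as 7 + 5 = 12 days after an injection. In later cycles, with one injection per 21-day cycle, it could be 21 + 5 = 26 days. If the site itself first hears at the next visit, both clocks start then and the difference returns to about 4 days.

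**The case against.** The strongest reply is that the literal reading is not the natural one. The sentence continues a bullet about hospitalizations. The quotation marks around the word admissions suggest that such a stay is simply not an inpatient admission. The section says that it clarifies Section 9.2, where any one criterion is enough. Section 4.2.2 also allows the Sentinel patient to be kept overnight, so there is good reason not to count a short stay as hospitalization. A careful investigator would still report a life-threatening event within 24 hours. This largely stands as a statement of intent. It does not remove the ambiguity, because the bullet says that such events, not merely such stays, go to the eCRF, and the next bullet shows that an exception was written where one was wanted.

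A reader might also infer more than the documents support:
- *That life-threatening events are barred from SAE reporting.* They are not. Section 9.2 still makes them serious. The two sections conflict, and the conflict permits a missed report without requiring one.
- *That nothing else would bring the event to notice.* The routes listed in the working exist. They lack a 24-hour limit, but they are real.
- *That most of the interval before the next injection would pass without contact.* After the first dose there is a visit on Day 2 and a call on Day 3. No such contacts are scheduled after the Day 8 and Day 15 injections.
- *That severe reactions in general would be lost.* Table 9 calls for hospitalization for Grade 3 and 4 atezolizumab reactions, and Table 2 mentions an intensive care setting for Grade 3 and 4 CRS. Many such cases would be inpatient and so serious anyway.
- *That the stopping rules or dose finding would fail.* The events in Section 4.5 and the DLT definition in Section 4.2.4 do not require SAE status.
- *That the reactions would vanish from the analysis.* A qualifying event would still appear in the DLT, Grade 3 or higher, and special-interest tables (SAP Tables 21, 29-31 and 40). The undercount is confined to the serious label in Tables 26-28.

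**Conclusion.** The point holds as a conflict between Sections 9.2 and 9.2.1. As worded, the bullet permits a serious acute reaction that is reversed in an emergency room or short-stay unit to be recorded on the eCRF only. For such an event, Sponsor notice could come about 4 days later than the SAE limit, and the event could miss SUSAR identification and SAP Tables 26-28.

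The number of events affected is probably small. The gap needs three things together: the event meets a criterion other than hospitalization, the patient is not admitted as an inpatient, and the investigator reads the bullet literally. The documents give no rate for any of these, so the number cannot be estimated. The 5-day figure is an expectation, not a limit, so the delay is indicative. The primary endpoint and the dose-escalation rules are not affected. The correction is worth making because it concerns prompt safety notice in a first-in-human trial and costs very little.

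**What to change.** Reconcile Sections 9.2 and 9.2.1 by rewording the bullet. It should say that an emergency room visit or a 23-hour observation stay does not by itself count as inpatient hospitalization, but that the event is reported as an SAE within 24 hours if it meets any other Section 9.2 criterion. The overdose bullet already supplies the model for the exception.

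If the narrow meaning was intended, this only states it. Short stays for observation or convenience would still not become SAEs. The SAP needs no change, because it has no SAE definition of its own. The cost is one clause in the protocol and possibly a few more SAE reports. No dose, schedule or treatment rule is touched.
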